5.1. Introduction

This study will randomize 230 participants; 115 will be randomly assigned to each of the two treatment arms (PREVENT and EUC). Note that only 156 participants were randomized due to the pandemic (78 participants to each of the two treatment groups). A participant is considered to be enrolled in the study (i.e., eligible for a baseline assessment) when all of the following conditions are met: (1) the participant meets screen criteria (aged 40+, African American race, in the ED, no diagnosis of dementia); and (2) provides written informed consent. A participant is considered to be eligible for randomization if they meet all eligibility criteria.

Recruitment, enrollment, consent, and the administration of Part 1 of the baseline assessment (to be performed prior to randomization) will be carried out by ED staff or the Outcome Assessor. Staff are stationed in the ED where they identify all patients who enter the ED. They prospectively monitor patient care by review of the computerized medical records to ascertain whether or not patients meet criteria for enrollment in the proposed trial.

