13.1. Data Analyses

We will use descriptive statistics to characterize the sample, assess randomization success, and as a final data quality check. We will analyze survey metrics (e.g., treatment satisfaction with PREVENT and EUC) by summing responses across items and reporting means and SDs. For outcome analyses, we will use an intent-to-treat approach (i.e., all participants with any follow-up data are included as randomized). Any missing data are considered missing at random (MAR); we will apply models that yield valid estimates under this assumption. For analyses of continuous outcomes, we will check assumptions of normality and homoskedasticity of errors using checks of model residuals. We will transform outcomes as appropriate prior to analyses and will use SPSS, SAS, TreeAge Pro, and Mplus software as indicated.

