13.1.1. Primary Aim

Test the efficacy of PREVENT to reduce the number of incident DM-related ED visits and/or hospitalizations over 12 months (primary outcome). Hypothesis: PREVENT will halve the number of incident DM-related ED visits and/or hospitalizations relative to EUC over 12 months.

Primary Statistical Approach: The primary outcome measure is a count of DM-related ED visits and/or hospitalizations. We will use Poisson regression to model the number of outcome events as a function of randomization assignment, adjusting for the stratification variables and using follow-up time as the offset term. We will consider baseline variables (e.g., age, sex, education, cognitive functioning, insurance, polypharmacy (i.e., taking ≥ 5 medications), and medical comorbidity) as possible covariates if they relate to outcome events at the bivariate level with p<0.2. Negative binomial regression will be considered if there is evidence of over- or under-dispersion of the data.] From the model, we will calculate estimates of annual rates of the primary outcome and the adjusted estimate of the rate ratio. We will evaluate the primary hypothesis by testing the null hypothesis that the rate ratio for randomization assignment equals 1.

To examine the impact of treatment adherence on outcomes, we will calculate the Complier Average Causal Effect (CACE) and compare it to the intent-to-treat estimate. We will define adherent participants as those who: 1) receive ≥ 4 of 9 treatment sessions, and 2) have a telehealth visit with the PCP, and 3) achieve ≥ 2 DM self-care treatment goals. CACE will estimate treatment effects by comparing the outcomes in adherent PREVENT participants vs. EUC participants who would have been adherent had they been assigned to PREVENT. The adherence status for EUC participants, however, is not observable. Through the use of a latent class model, the CACE is estimable under certain assumptions. Part of the model includes using baseline covariates and adherence status in PREVENT participants to predict adherence status in EUC participants. This analysis will enable us to estimate the impact of adherence on study outcomes.

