Analysis: We will use structural equation modeling (SEM) to evaluate this aim, and will simultaneously model the DM-related ED visit/hospitalization count and each proposed mediator separately (i.e., PSQ-18 scores, number of received Diabetes Quality Metrics, and DSCI scores). The model will have paths from treatment to ED visit/hospitalization count (direct effect), treatment to mediator, and mediator to ED visit/hospitalization count. Using MPlus software, we will fit the SEM model and calculate the total indirect effect for the mediator. Mediation of the treatment effect on reduced incidence of DM-related ED visits and/or hospitalizations will be considered present if there is a significant path from treatment through the mediator to the primary outcome (i.e., an indirect effect). Standard errors will be calculated using bootstrapping. If there is evidence of mediation for more than one of the proposed mediators, we will fit a model that simultaneously considers the effect of the multiple mediators.

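### The mediation test in Aim 4 bootstraps only the standard error and names no interval; on its natural reading it is conservative and loses power at n=156

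*Combined protocol and SAP*

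**What the plan says.** Under Secondary Aims in section 13.1.1 (Aim 4, Analysis), the event count is modelled jointly with "each proposed mediator separately (i.e., PSQ-18 scores, number of received Diabetes Quality Metrics, and DSCI scores". On software and target quantity: "Using MPlus software, we will fit the SEM model and calculate the total indirect effect for the mediator". The decision rule is that mediation "will be considered present if there is a significant path from treatment through the mediator to the primary outcome". The bootstrap appears once: "Standard errors will be calculated using bootstrapping". A joint model of several mediators follows only if more than one of them shows evidence of mediation.

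The text does not say how significance is judged. It lists three paths (treatment to outcome, treatment to mediator, mediator to outcome) and names no baseline covariates for them.

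On the data: "The primary outcome measure is a count of DM-related ED visits and/or hospitalizations" (section 13.1.1, Primary Aim). On size: "Note that only 156 participants were randomized due to the pandemic (78 participants to each of the two treatment groups" (section 5.1), against a planned 230. Outcome analyses use an intent-to-treat set in which "all participants with any follow-up data are included as randomized" (section 13.1), so the usable number may be below 156.

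**The concern.** A yes/no criterion resting on significance, paired with nothing but a standard error, would ordinarily be applied as estimate over standard error against 1.96. That works for a roughly normal estimate. An indirect effect is the product of the treatment-to-mediator path (a) and the mediator-to-outcome path (b). In small samples its distribution is skewed away from zero, so a symmetric interval reaches too far towards zero. The resamples drawn for the standard error already carry the right shape, but the stated use discards it.

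At stake is a numbered secondary aim with its own hypothesis, meant to explain how PREVENT works and now run on about two thirds of the planned sample (156/230 = 68%). A conservative rule makes real mediation harder to declare. It also carries into the joint model, which needs at least two mediators to pass. As an illustration, if two mediators were independent, both would pass 0.41² = 17% of the time at 41% power each, and 0.63² = 40% at 63% power each.

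**Working it through.** **No figure to reproduce.** The plan gives no power, path size, event rate, dispersion or alpha for Aim 4. The inputs from the documents are n = 156 (78 per arm), a count outcome, and mediators first tested one at a time. Everything else below is assumed, with alpha 0.05 two-sided.

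**The two rules compared**, both from the same resamples:
- z-rule: reject if |a·b| / SD_boot(a·b) > 1.96.
- Percentile rule: reject if the interval from the 2.5th to the 97.5th percentile of the resampled a·b excludes 0.

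**Why they differ.** Scale each path by its standard error, giving z_a and z_b, and treat the two as independent and normal. The bootstrap SD of the product is then √(z_a² + z_b² + 1). Take z_a = z_b = 2.5:
- z-rule: 2.5² / √(2·2.5² + 1) = 6.25 / 3.674 = 1.70, which is not significant.
- Percentile rule: the share of resampled products on the wrong side of zero is 2·Φ(−2.5)·Φ(2.5) = 2 × 0.0062 × 0.9938 = 0.012. This is below 0.025, so the interval excludes zero.

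With equal paths, setting the first expression to 1.96 gives z = 2.86, and setting the second to 0.025 gives z = 2.24. The z-rule therefore needs both paths to be clearly stronger.

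**Simulation at n = 156.** Assumed: normal mediator, baseline rate 1 per year, direct effect −0.3 on the log rate, and a Poisson or negative binomial (dispersion 1) count analysed by Poisson regression on treatment and mediator. There were 1,000 data sets per scenario and 500 resamples each. Path a is in SD; path b is log rate per SD. Negative binomial results:

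| a | b | z-rule | Percentile | Gap (points) |
|---|---|---|---|---|
| 0.3 | −0.2 | 3.3% | 16.0% | 12.7 |
| 0.3 | −0.4 | 21.9% | 40.6% | 18.7 |
| 0.4 | −0.3 | 22.7% | 45.9% | 23.2 |
| 0.4 | −0.4 | 38.0% | 59.8% | 21.8 |
| 0.5 | −0.4 | 57.8% | 78.6% | 20.8 |
| 0.5 | −0.6 | 78.8% | 88.3% | 9.5 |
| 0.6 | −0.6 | 91.0% | 96.0% | 5.0 |
| 0.8 | −0.6 | 98.0% | 98.9% | 0.9 |

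Over all 40 scenarios (a from 0.3 to 0.8, b from −0.2 to −0.6, dispersion 0 or 1) the gap ran from 0.1 to 23.2 points and always favoured the percentile rule; 25 of the 40 gaps were 10 points or more. In the 18 scenarios with a ≤ 0.5 and |b| ≤ 0.4 it ran from 9.4 to 23.2. Monte Carlo error on a gap is about 1 to 1.5 points.

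**Type I error.** With one path zero, the z-rule rejected 1.5% to 1.8% of the time and the percentile rule 4.6% to 5.0%. With both paths zero, both rejected 0.0%.

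**Checks.** A normal-theory grid over the two path noncentralities gave gaps of 0 to 25 points, largest (about 23 to 25) when both were about 2.5 to 3. A simulation with other assumptions (EUC rate 1.5 per year, gamma frailty variance 0.5, Monte Carlo error about 2.5 points) gave, z-rule against percentile:
- a = 0.3, b = −0.3: 18% vs 37%
- a = 0.4, b = −0.3: 41% vs 63%
- a = 0.5, b = −0.3: 52% vs 74%
- a = 0.4, b = −0.4: 58% vs 69%
- a = 0.5, b = −0.4: 74% vs 87%

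None of these runs includes attrition, stratification covariates or the follow-up offset.

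**The case against.** **No z-test is written down.** A reader might infer that the plan prescribes one. It does not: it asks for significance and bootstraps the standard error, and the same words would allow another rule. What the text supports is an unspecified rule whose natural reading is the weaker test.

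**The size is not in the documents.** A reader might attach one fixed loss to the plan, such as the 11 to 22 points spanned by the five scenarios just listed. That range depends on the paths chosen; 16 of the 40 wider scenarios fell below 11 points. The primary hypothesis is a halving (log rate ratio −0.69). Indirect effects of 0.3 × 0.3 = 0.09 to 0.5 × 0.4 = 0.20 carry only 13% to 29% of it, and if one mediator carried most of the effect the gap would be small. Three mediators may, however, share the effect, so moderate paths are not implausible.

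**A conservative test is still valid, and the margin has uses.** This is the strongest objection. With no mediator effect but an unmeasured common cause of mediator and outcome (assumed coefficients 0.3 to 0.4), the unadjusted three-path model declared false mediation in 12%, 25% and 33% of trials with the percentile rule, against 4%, 8% and 16% with the z-rule. With three independent null mediators, at least one false positive occurs 1 − 0.95³ = 14% of the time at 5% each, against 1 − 0.982³ = 5% at 1.8% each. Both points stand as costs of the change. They do not justify the z-rule: confounding invalidates either test, and an accidental loss of power is not a multiplicity plan.

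**Mediation will still be missed after the change.** This is true: at a = 0.4 and b = −0.4 in the table, the percentile rule misses about 40%. The change recovers part of the power and does not make Aim 4 well powered.

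**Conclusion.** The concern holds in a conditional form. The plan uses the bootstrap for standard errors only and leaves the mediation decision rule unstated. If the rule is estimate over bootstrap standard error against a normal, type I error is about 1 to 2% with one path zero. Power at n = 156 is then lower than with a percentile interval by roughly 10 to 25 points for small-to-moderate paths, and by little for strong ones. The direction was the same in every scenario run; the size rests wholly on the assumed paths, rate, dispersion and alpha. The documents support neither the claim that a z-test is prescribed nor a single figure for the loss. The change is worth making: it is cheap, it settles the rule, and with mediator-outcome confounding absent or adjusted for, the percentile interval kept rejection at about 5% or below for each mediator.

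**What to change.** Replace the bootstrap sentence in the Aim 4 analysis with wording such as: each indirect effect will be tested and reported with a 95% bootstrap percentile confidence interval (for example 5,000 resamples), and mediation will be considered present if the interval excludes zero.

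Add a second sentence: the mediator and outcome paths will include the baseline value of the mediator and the baseline covariates already collected. Table 5 lists all three mediators at baseline as well as follow-up, together with the potential covariates. This limits the extra confounded findings that a sharper test would pick up, but cannot remove confounding by unmeasured factors. With three mediators tested separately, the report should also say whether the intervals are adjusted for multiplicity.

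The cost is two sentences and some computing time. The planned software can stay and no new data are needed. The number of resamples is a new commitment, since the plan gives none. What is given up is the z-rule's conservative margin. The change should be fixed before the mediation results are seen.

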13.1.3. Exploratory Aims

- 1. Determine whether PREVENT reduces "all cause" ED visits/hospitalizations relative to EUC. Analysis: We will use the Poisson regression approach described in the analysis of the primary aim.
- 2. Determine if Community Need Index score, literacy, age, and/or sex moderate treatment effects. Analysis: We will explore moderation effects by extending the models above to include randomization assignment by moderator interaction terms, and estimating treatment effects for different levels of the moderator. We will consider treating the moderators as continuous variables under a linear assumption, and as categorical variables categorized in clinically meaningful ways, by quartiles, or at the median. As the literature on sex differences on ED use in AAs is scant, we are unable to formulate specific hypotheses regarding the relationship of sex to study outcomes. If our data suggest differences by sex, we will conduct supplementary analyses to delineate potential

mediators of these differences. We will also examine whether "built environment" indicators (i.e., neighborhood safety, transportation difficulties, and access to healthy foods) moderate treatment response.

- 3. Determine if PREVENT improves glycemic control (i.e., lowers HbA1c levels), impacts DM-related Health Beliefs, reduces depression, and/or improves quality-of-life.

 Analyses: For these continuous outcomes we will use the mixed effects approach described above.
- 4. Identify the treatment features of PREVENT which confer its cultural relevance. Analysis: We will use descriptive statistics to characterize responses on the Cultural Relevance Rating Form in participants assigned to PREVENT. If ≥ 75% of participants rate an item ≥ 7 [from 1 to 10 (more valued], that aspect of treatment will be considered to be culturally relevant.
- 5. Evaluate PREVENT's costs and net financial benefit.

Analysis: Intervention costs will be calculated using wage rates multiplied by time in preparation, documentation, delivery, training, and supervision. Fringe benefit costs will be added to staff member costs by application of prevailing rates. Material costs will include study documentation forms and educational materials. Travel expenses to/from participant homes will be captured per visit, and will be costed using current government reimbursement rates. We will estimate direct medical costs using published reimbursement rates (e.g., Medicare) for inpatient and outpatient care. The costs of DM-related ED visits and hospitalizations will be captured at baseline and months 6 and 12 for both treatment groups. Costs for DM outpatient services will be based on Medicare reimbursement rates using relevant CPT codes. We will define net financial benefit as the difference between total costs of PREVENT vs. EUC. We will conduct sensitivity analyses to determine the robustness of this calculation. The results will reveal ways to improve the efficiency of treatment delivery and to facilitate translation to practice. The sensitivity analyses will include those variables where we anticipate "real-world" uncertainty, and will include modification of key cost variables (e.g., inpatient and outpatient medical costs, based on 25th and 75th percentiles of Medicare reimbursement.)

14: STUDY TIMELINE

The Start-Up phase will take place during the first 6 months of the trial. The following will occur during the Start-Up phase: (1) hiring and training of study staff; (2) refining and implementing procedures for study recruitment; (3) creating study data files and exporting all data collection instruments into REDCap; (4) creating the randomization schedules; (5) updating the Resource List (to provide social service referrals to participants if needed); (6) creating administrative forms and study letters (e.g., to inform participants of eligibility status); and (7) convene a meeting with the DSMB and have the DSMB review and approve relevant study materials. Recruitment will take 20 months (months 7 through 26). We will expect to conduct 15 baseline assessments per month, and randomize 11 to 12. The initial 6 treatment sessions will be administered during months 7 through 32. The 6 month follow-up (FU) assessments will take place months 13 through 48 will be devoted to data cleaning and analysis, and dissemination of study findings.

	Year 1					Year 2				Year 3					Year 4								
2	4	6	8	10	12	14	16	18	20	22	24	26	28	30	32	34	36	38	40	42	44	46	48
STA	ART I	JP																					
			BAS	SELII	NE A	SSES	SSME	ENTS															
			6 IN	IITIA	L INT	ERV	ENTI	ON S	ESS	ONS	OVE	R 4 I	MONT	HS									
					3 B	OOS	TER	SESS	SIONS	S AT	6. 8.	AND	10 M	ONTI	HS.								
						6 M	ONT	H FU	ASS	ESS	MEN'	TS I		T	I								
									12 I	MON	TH F	U AS	SESS	SMEN	ITS								
																						NALY INAT	'SIS; ION

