PREVENT will begin soon after the participant's index ED visit, when many patients remain uncertain how to manage DM or how to access follow-up care. Community Health Workers (CHWs), who are race-concordant with participants, will: 1) deliver in-home DM education to increase participants' knowledge and skills; 2) use DM-specific Behavioral Activation to improve DM self-care; and 3) facilitate telehealth visits with the participant's primary care physician (PCP) and a DM nurse educator to increase access to care. The control treatment, EUC, is usual medical care that is enhanced with DM self-care education. EUC matches PREVENT in treatment intensity (i.e., 6 in-home sessions over 4 months, and 3 booster sessions over the next 8 months) and delivery of culturally relevant DM education, but does not include DM-specific Behavioral Activation or telehealth visits. The treatment comparison will identify PREVENT's specific efficacy over and above EUC.

This RCT is significant as the population ages and becomes more racially diverse, and as ED use and costs increase. This RCT is innovative because it: 1) tests the first ED-to-community intervention designed to reduce the need for ED care in AAs with DM; 2) assesses both subjective and objective indicators of access to care; and 3) defines the specific characteristics of PREVENT that confer its cultural relevance. If successful, PREVENT will meet Healthy People 2020's twin goals of reducing the personal and societal costs of DM and achieving health equity for all Americans.

The Specific Aims of this RCT are:

Primary Specific Aim: Test the efficacy of PREVENT to reduce the number of incident DM-related ED visits and/or hospitalizations over 12 months (primary outcome) in AAs with DM. Hypothesis: PREVENT will halve the number of incident DM-related ED visits and/or hospitalizations relative to EUC over 12 months.

The Secondary Aims are to:

- 1. Test the efficacy of PREVENT to increase perceived access to care over 12 months (secondary outcome). Hypothesis: PREVENT will increase Patient Satisfaction Questionnaire-18 scores to a greater extent than EUC over 12 months.
- 2. Test the efficacy of PREVENT to increase realized access to care over 12 months (secondary outcome). Hypothesis: PREVENT will increase the number of received Diabetes Quality Metrics (e.g., hemoglobin A1c testing, urine screening) to a greater extent than EUC over 12 months.

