- 3. Test the efficacy of PREVENT to improve DM self-care over 12 months (secondary outcome). Hypothesis: PREVENT will increase Diabetes Self-Care Inventory scores to a greater extent than EUC over 12 months.
- 4. Determine if increasing subjective and/or objective indicators of access to care and/or DM self-care mediates PREVENT's reduction of DM-related ED visits and/or hospitalizations. Hypothesis: PREVENT will reduce DM-related ED visits and/or hospitalizations to the extent that it increases subjective and/or objective indicators of access to care and/or improves DM self-care.

The Exploratory Aims are to: 1) determine whether PREVENT reduces "all cause" ED visits/hospitalizations relative to EUC.; 2) determine whether Community Need Index scores, literacy, age, and/or sex moderate treatment effects; 3) determine if PREVENT improves glycemic control (i.e., lowers hemoglobin A1c levels), impacts DM-related health beliefs, reduces depression, and/or improves quality-of-life; 4) identify PREVENT's treatment features that confer its cultural relevance; and 5) estimate PREVENT's costs and net financial benefit to the healthcare system.

2: RESEARCH DESIGN SUMMARY

A. Study Purpose and Rationale: This Phase-III RCT will compare the efficacy of Community Care to Prevent Diabetes Emergencies (PREVENT) vs. Enhanced Usual Care (EUC) to reduce incident DM-related ED visits and/or hospitalizations over 12 months in 230 African Americans with diabetes (aged 40 and older), following an ED visit for a DM-related condition. Note that only 156 participants were randomized.

- B. Study Design: This study is a randomized controlled clinical trial in which the unit of randomization is the person. Participants will be randomized 1:1 to PREVENT (the experimental treatment) or EUC (the control condition).
- C. Sample: The sample will comprise 230 older persons (only 156 were randomized) who meet the following criteria:

Inclusion criteria:

- 1) African American race (self-identified)
- 2) Age ≥ 40 years
- 3) Type 1 or 2 DM
- 4) A recent ED visit

Exclusion criteria:

- 1) Diagnosis of dementia
- 2) Anti-dementia medication use
- 3) Life expectancy less than one year (in the opinion of the evaluating ED physician)
- 4) DSM-V psychiatric disorders other than anxiety or depression (as per EMR)
- 5) Intoxicated
- 6) Suicidal
- 7) In police custody or currently incarcerated

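### The planned robustness check on net financial benefit carries no sampling error, so a chance saving in 78 participants per arm can survive the price scenarios

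*Combined protocol and SAP*

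**What the plan says.** The aim, listed in section 1, is to "estimate PREVENT's costs and net financial benefit to the healthcare system". Section 13.1.3, aim 5, defines the quantity: "We will define net financial benefit as the difference between total costs of PREVENT vs. EUC". Programme costs are built from staff time: "Intervention costs will be calculated using wage rates multiplied by time in preparation, documentation, delivery, training, and supervision". Medical costs are priced from published reimbursement rates.

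On uncertainty, the same paragraph says: "We will conduct sensitivity analyses to determine the robustness of this calculation". It adds that these analyses will cover inputs expected to be uncertain in practice, and it gives one class of them as an example: "and will include modification of key cost variables (e.g., inpatient and outpatient medical costs, based on 25th and 75th percentiles of Medicare reimbursement". No other variable is named.

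No standard error, confidence interval, bootstrap or probabilistic analysis of the cost difference appears anywhere. Section 6.2 (Intervention Costs) promises good health-economic practice without naming a method. Section 12.2.2 lists TreeAge Pro without saying how it will be used. The one bootstrap in the plan belongs to the mediation analysis (Secondary Aim 4). No criterion for calling the result robust is given.

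**The concern.** The estimate depends on how many ED visits and admissions happen to fall in each arm, and only 78 people were randomized to each (section 5.1). Re-pricing those same events shows how the answer depends on prices. It does not show whether the difference in events could be chance.

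The case where this matters most is plausible here. Section 1 states that "EUC matches PREVENT in treatment intensity", so the two programmes may differ only modestly in cost, and the result then turns mainly on the event difference. A reader told that a saving held at low and high prices could take it as established when the events differ only by chance. Section 13.1.3 expects these results to help move the programme into practice, so that reading has consequences even for an exploratory aim.

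**Working it through.** The documents give no cost figure, cost SD or interval for this aim, so there is no stated figure to reproduce. The check asks how often a saving survives price changes when there is no true effect on events.

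**Inputs from the documents.** 78 per arm (section 5.1); hypothesised halving of events (section 13.1.1, Primary Aim); overdispersion considered possible, no value given (same section).

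**Assumed inputs.** Control event rate μ = 0.4, 0.8 or 1.2 per year; negative binomial dispersion k = 0, 1 or 2; medical prices varied by p = ±25% or ±50%; extra programme cost c = 0, 0.05, 0.1 or 0.2 of one event price. One price applies to all events, and costs do not vary between events.

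**Identity.** Let d be events avoided per participant. Net saving, in event prices, is d − c. A saving survives both price scenarios if d(1−p) > c. The sign changes across prices only if c/(1+p) < d < c/(1−p). If c = 0, or if d ≤ 0 with c > 0, a common price factor cannot change it.

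**Sampling error.** With no true effect, SE(d) = √[2(μ + kμ²)/78]. For μ = 0.8, k = 1: √(2 × 1.44/78) = 0.192. Over k = 0 to 2, SE(d) is 0.10 to 0.14 at μ = 0.4, 0.14 to 0.23 at μ = 0.8, and 0.18 to 0.32 at μ = 1.2. The hypothesised reductions are 0.2, 0.4 and 0.6.

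**One case by hand** (μ = 0.8, k = 1, c = 0.1, p = 0.5). A saving survives if d > 0.1/0.5 = 0.2, and P(Z > 0.2/0.192) = 0.149. A 95% interval lies wholly above zero if d > 0.1 + 1.96 × 0.192 = 0.476, and P(Z > 2.48) = 0.007.

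**Simulation, no true effect** (40,000 trials per setting; range over μ, k and p):

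| Extra cost c | Saving survives price check | 95% interval shows a saving |
|---|---|---|
| 0 | 47% to 49% | 2.4% to 2.7% |
| 0.05 | 17% to 42% | at most 1.7% |
| 0.1 | 2% to 34% | at most 1.1% |
| 0.2 | 0% to 21% | at most 0.4% |

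The first row is symmetry: with no effect and equal programme costs, about half of chance differences favour PREVENT, and ties bring it just below half.

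**Dollar version, with costs varying between events** (assumed: 1 event per year, k = 1, mean $5,000 per event, CV 1.5, prices × 0.7 and × 1.3). The variance of a participant's cost is (2.25 + 2) × 5,000² = 106.25 million. The SE of the mean difference is √(2 × 106.25 million/78) ≈ $1,650. P(0.7 × difference > extra cost) is 0.50, 0.41, 0.33 and 0.19 at extra costs of $0, $250, $500 and $1,000. P(Z > 1.96 + extra cost/1,650) is 0.025, 0.017, 0.012 and 0.005.

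**With the hypothesised halving** (k = 0 or 1, prices ±50%). The sign stayed the same in 100% of trials at c = 0, 57% to almost 100% at c = 0.1, 24% to 90% at c = 0.2, and 10% to 77% at c = 0.4. Price scenarios are therefore informative when programme cost is close to the savings.

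**The case against.** Three stronger readings are tempting, and the documents support none of them.

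- A reader might infer that robustness is judged by unit prices alone. The text twice says what the analyses will include, and it offers the percentiles only as an example. That stands. But an open list commits nobody to an interval, and no other variable is named.
- A reader might infer that the sign of the result is practically fixed. That is exact only when programme costs are equal, or when the event difference is nil or adverse and PREVENT costs more. The estimand is total cost, and section 6.2 also counts outpatient and medication costs, which the model above leaves out. PREVENT aims to increase access to care, so outpatient and inpatient differences could point in opposite directions, and pricing them separately could reverse the sign.
- A reader might infer that the plan will call a chance saving robust. It contains no such rule. The survival rates above describe a rule assumed for the check.

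It is also fair that zero extra cost is unlikely. PREVENT adds one PCP and three nurse-educator telehealth visits (section 9.1) and supplies (section 4.3), so the lower rows of the table may be nearer the truth. Finally, the event counts get their own tested rate ratio, which would be read beside the cost result. That helps, but it gives no interval for the cost difference, which also contains programme, outpatient and medication costs.

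**Conclusion.** The point holds as a reporting gap in an exploratory aim. As written, the analysis gives a point difference and named checks on cost variables, and neither can separate a saving from chance with 78 per arm. Under the assumed inputs and no true effect, a saving survived the price changes in up to about half of trials at zero extra programme cost and in 0% to 21% when the extra cost was 20% of an event price. A 95% interval showed a saving in 2.7% at most. These rates rest on assumed event rates, dispersion, price ranges and cost ratios, and on the assumed survival rule. Cost variation between events, left out of the main simulation, would widen the interval further. The primary and secondary analyses are untouched.

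**What to change.** Keep the price scenarios as a separate deterministic analysis. Add a nonparametric bootstrap that resamples participants within arm, using each participant's total cost (programme plus medical). Report the mean cost difference with a 95% interval at base, 25th and 75th percentile prices. Describe the result as uncertain when the interval includes both a saving and a loss. There is no need to reserve the term net benefit for intervals that exclude zero, since this is an exploratory estimate. Name the other variables to be varied.

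The cost is a little more analysis on event and staff-time data that the plan already collects. The interval will probably be wide, and the claim less favourable.
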